5.2.5. Day 28 Visit (± 2 days)

- Physical examination and vital signs;
- Hematology;
- Biochemistry and urinalysis;
- Viral Load, CD4/CD8 count;
- Urine pregnancy test for all women of childbearing potential;
- 12 leads ECG,
- Blood collection for HIV reservoir assessment;
- Check treatment compliance;
- Adverse Events reporting;
- Stop all treatments (DRV/RTV or COBI + ABX464/placebo);
- Schedule next patient visits.

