A food effect trial was not conducted for COBI since it is coadministered with other antiretroviral agents under fed conditions, in accordance with the prescribing information for these agents. It is recommended that COBI coadministered with atazanavir or darunavir be administered with food.

Metabolism

COBI is metabolized by CYP3A and to a minor extent by CYP2D6 enzymes and does not undergo glucuronidation. COBI 150 mg provides near-maximal inhibition of CYP3A, as assessed using midazolam. These results were roughly in agreement with those obtained with ritonavir (in vitro studies utilizing human liver microsomes have demonstrated that CYP3A is the major isoform involved in RTV metabolism, although CYP2D6 also contributes to its biotransformation.

Overall, COBI a lower potential for off-target drug interactions than the standard boosting agent ritonavir, due to its more selective inhibition of CYP3A and lower likelihood for enzymatic induction, and is devoid of anti-HIV activity.

Elimination

The terminal plasma half-life of cobicistat following administration of COBI is approximately 3 to 4 h which is slightly lower than ritonavir (3 to 5 h). With single dose administration of 14C COBI after multiple dosing of COBI for 6 days, the mean percent of the administered dose excreted in feces and urine was 86.2% and 8.2%, respectively.

ABX464

After single oral administration of 50 to 200 mg ABX464, ABX464 is relatively quickly absorbed and undergoes a very extensive biotransformation into its N-glucuronide metabolite, NGIc.

In most of the subjects, regardless of the dose, ABX464 plasma concentrations is generally not measured after 8 to 10 h post-dose. Cmax is generally observed within the first 2 h post-dose and then ABX464 plasma concentrations decreased with a t1/2 of about 1 to 2 h.

NGlcABX464 plasma concentrations were markedly higher than those of the parent drug with mean Cmax about 200 to 300-fold higher than ABX464 Cmax. Cmax was observed around 4 h post-dose with a very limited variability thereafter ABX464NGlc was slowly eliminated and had a t1/2 of 90 to 110 h.

Relationship between rate and extent of absorption of ABX464 and ABX464 dose is quite erratic with a reduced increase with the dose up to 150 mg and a saturation like behavior at 200 mg.

NGIcABX464 exposure-dose relationship is somehow comparable to that of ABX464 although increase of Cmax and AUCs tend to be dose proportional between 50 and 150 mg.

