8.1. Definition of an AE

Any untoward medical occurrence in a patient or clinical investigation patient administered a pharmaceutical product and which does not necessarily have to have a causal relationship with this treatment.

An AE can therefore be any unfavorable and unintended sign (including an abnormal laboratory finding), symptom, or disease (new or exacerbated) temporally associated with the use of a medicinal product, whether or not considered related to the medicinal product.

Note: The official definition also extends to AEs occurring in the placebo arm. Because of regulatory requirements, events occurring during pre-and post-treatment periods will also be designated as AEs. Therefore, reporting of such events, AEs and SAEs, will commence when the patient is enrolled into the study (date of signature of the informed consent) up until 4 weeks after the end of the treatment visits. The period after discontinuing study drug may be extended if there is a strong suspicion that the drug has not yet been eliminated.

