8.3. Events or Outcomes Qualifying as AEs or SAEs

8.3.1. Clinical laboratory parameters

Abnormal laboratory findings (e.g., clinical chemistry, hematology) or other abnormal assessments (e.g. vital signs) that are judged by the investigator as **clinically significant** will be recorded as AEs or SAEs if they meet the definitions of sections 8.1 and 8.2 respectively. Clinically significant abnormal laboratory findings or other abnormal assessments that are detected during the study or are present at informed consent and significantly worsen during the study will be reported as AEs or SAEs. Clinically significant abnormal laboratory findings or other abnormal assessments that are associated with the disease being studied, and are present at the start of the study but do not worsen, will **not** be reported as AEs or SAEs. However, if these findings or assessments are judged by the investigator to be more severe than expected considering the patient's condition, then they may be reported as AEs or SAEs.

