9.3. Safety Analyses

Adverse events will be coded using the standard dictionary (MedDRA) down to the lower level term (LLT).

An overall summary table will be presented (Any adverse event, any treatment emergent adverse event (TEAE), any serious adverse event (SAE), death, any grade 3 or higher adverse events from baseline to the end of Study. This analysis will be conducted on SAF population.

Two periods will be defined for TEAE:

- Any adverse event which occurs or worsens from first dosing to Day 28;
- Any adverse event which occurs after Day 28.

Adverse events will be described by primary system organ class and preferred term. Numbers and percentage of patients, and number of occurrence of adverse event will be presented for:

- TEAE;
- Serious TEAE;
- TEAE leading to drug discontinuation;
- TEAE of grade 3 or 4;
- TEAE for which relationship with the study drug is recorded as possible or probable.

The assessment of safety will be based on the frequency of adverse events (with and without regard to causality) graded according to the "Division of AIDS table for grading the severity of adult and pediatric adverse events" (December 2004) and also, the review of individual values for clinical laboratory data, vital signs and ECG focusing on the detection of abnormal values and PCSAs [potentially clinically significant abnormalities (PCSAs) determined upon investigator considerations].

Adverse events will be tabulated (counts and percents) by group. All adverse events will be listed and the data will be tabulated by body system/organ class. Adverse event tabulations will include all treatment emergent adverse events, which will be further classified by severity, and relationship to treatment and dose level.

Clinical laboratory parameters, vital signs, ECG will be summarized by using descriptive statistics (n, mean, SD, SEM, median, minimum and maximum). Number of patients with at least one abnormal values will be tabulated (counts and percents) for each parameter in summary shift tables, by group and dose.

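### The post-treatment TEAE period in protocol 9.3 omits worsening and is cut at nominal Day 28, so some adverse events are shown in the wrong period or in neither

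*Protocol*

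**What the plan says.** Section 9.3 (Safety Analyses) sets two TEAE periods:

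- Period 1: "Any adverse event which occurs or worsens from first dosing to Day 28".
- Period 2: "Any adverse event which occurs after Day 28".

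The first rule is met by onset or by worsening. The second is met by onset only.

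The same section plans an overall summary table that includes "any grade 3 or higher adverse events from baseline to the end of Study". It also plans tables of TEAEs by organ class and preferred term, one of them for "TEAE of grade 3 or 4", and a listing of all adverse events.

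Elsewhere the protocol treats worsening as reportable. The definition in 8.1 covers a "symptom, or disease (new or exacerbated) temporally associated with the use of a medicinal product". Under 8.3.1, clinically significant abnormal findings that "are present at informed consent and significantly worsen during the study will be reported as AEs or SAEs".

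On timing, the Day 28 visit in 5.2.5 carries a window of ± 2 days and includes the instruction "Stop all treatments (DRV/RTV or COBI + ABX464/placebo"). Section 7.2 lets a patient leave the study at any time and requires withdrawal for a defined rise in liver enzymes. Section 8.4 collects adverse events from consent until 4 weeks after study drug is completed or discontinued.

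**The concern.** Safety against placebo is the primary objective (2.1). The end of treatment is an unusual boundary here because study drug and all antiretroviral therapy stop together. Splitting TEAEs at that point should separate what happens on study drug with background therapy from what happens off both. A post-treatment period that admits onset but not worsening does this only in part.

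The protocol itself expects effects after the stop. Section 3.2 asks for liver function tests for at least 28 days after interruption. Section 8.1 allows adverse event collection to be extended if the drug may not have been eliminated. Section 5.3.7 reports that the main metabolite "was slowly eliminated and had a t1/2 of 90 to 110 h".

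At stake is whether the by-period safety tables place late worsening, and the grade it reaches, on the correct side of treatment stop.

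**Working it through.** The plan gives no figure to reproduce. The check applies the two rules in 9.3, as worded, to each pattern of onset and worsening.

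| Onset | Worsening | Period 1 | Period 2 |
|---|---|---|---|
| First dose to Day 28 | none | yes, by onset | no |
| First dose to Day 28 | by Day 28 | yes | no |
| First dose to Day 28 | after Day 28 | yes, by onset | no: the worsening has no place |
| After Day 28 | any | no | yes, by onset |
| Before first dose | by Day 28 | yes, by worsening | no |
| Before first dose | first after Day 28 | no | no |

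**Row 3: attribution.** Take an event that starts on Day 21 and reaches grade 3 on Day 35. Its onset puts it in period 1. Day 35 lies inside the collection window, which runs to Day 28 + 28 = Day 56 for a patient whose last dose is on Day 28. The rules give period 2 no claim on the rise to grade 3. If the event is tabulated once with its worst grade, grade 3 appears as an on-treatment grade although it was reached 7 days after the stop.

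**Row 6: a literal gap.** A condition present before first dose that first worsens on Day 35 meets neither rule. If the worsening is entered as a new adverse event dated Day 35, it occurs after Day 28 and enters period 2. The outcome therefore depends on how the site records it, and 9.3 does not say.

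**Recording.** Section 8.5 asks for a start date, a stop date and a severity for each event. It asks for a fresh entry when the same event occurs on several occasions. It requires no date for a change of grade within one continuing event. If the form follows that list, the later analysis may be unable to place the change.

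**Nominal cut.**
- *Early stop.* For a patient who stops study drug on Day 10, collection runs to Day 10 + 28 = Day 38. Days 11 to 28 are 18 of those 28 off-drug days, and events starting then fall in period 1.
- *Stop visit off Day 28.* With a window of ± 2 days, a stop on Day 26 puts up to 2 off-drug days in period 1. A stop on Day 30 puts up to 2 on-drug days in period 2, if dosing continues to that visit.

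**Is delayed worsening plausible?** The fraction of metabolite remaining at time t after the last dose is 2^(−t/half-life), assuming first-order decline.
- At 7 days (168 h): 2^(−168/90) = 0.27 and 2^(−168/110) = 0.35.
- At 14 days (336 h): 2^(−336/90) = 0.075 and 2^(−336/110) = 0.12.

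So 27–35% remains after one week and 8–12% after two. This shows that drug-related worsening after the stop is possible. It does not measure how many events would be misplaced.

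**The case against.** The strongest reply is that little is at risk, and most of it holds.

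- A reader might infer that an event starting on drug and turning severe after the stop is counted in neither period. The text does not support that. Onset and worsening are alternatives in period 1, so onset alone is enough.
- A reader might infer that the severe grade is lost. It is not: the summary of grade 3 or higher events runs to the end of the study, all events are listed, and laboratory worsening also appears in the by-visit statistics and shift tables of 9.3 and 9.3.1. The protocol does not say that the worst grade is the one recorded, but nothing in it discards that grade.
- A reader might infer that the serious, grade 3 or 4 and related TEAE tables are all split by these periods. Section 9.3 lists those tables without saying whether they are split or pooled.
- Because worsening counts as an adverse event under 8.1 and 8.3.1, a site may enter a late exacerbation as a new event, which closes the gap for that event. This mitigates the problem but is not a stated rule.
- Section 9 leaves technical detail to the SAP, which is not shown. How a grade change is counted could properly be settled there. The period definitions themselves, however, are fixed in the protocol, and they differ in a way that the SAP would have to override rather than elaborate.
- Day 28 is the planned last day of dosing, so the nominal cut is right for patients who follow the schedule. It fails only for those who do not.

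**Conclusion.** The defect is real but minor. As written, worsening after Day 28 cannot enter the post-treatment period. Three consequences follow:

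1. A grade reached off drug and off antiretrovirals can be displayed as an on-treatment grade.
2. A pre-dose condition that first worsens after Day 28 falls in neither period, unless it is recorded as a new event.
3. The nominal cut misplaces events for early stoppers, and by up to 2 days for patients whose stop visit is off Day 28.

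The protocol gives no basis for estimating how many events are affected. One patient among 21 on ABX464 is 1/21 = 4.8 percentage points, but that is the weight of any single patient and not the size of this problem. The first consequence assumes that an event is tabulated once at its worst grade. The second assumes that the worsening is not given its own record. The third, for a late stop visit, assumes that dosing continues to that visit.

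**What to change.** Reword the two rules in 9.3:

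- Period 1: adverse events that start, or worsen in grade, from the first dose to the last dose of study drug (ABX464 or placebo).
- Period 2: adverse events that start, or worsen in grade, after the last dose of study drug.

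Add that a grade increase after the last dose is counted in period 2 at the grade reached, and have its date captured, for example by opening a new adverse event record when a continuing event worsens across the boundary.

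The cost is small: a rewording in 9.3 and an instruction for completing the adverse event form, with no extra visits. The downside is that one event can appear in both periods, so period counts may add to more than the number of distinct events. A footnote and an overall column that counts each event once would deal with that.

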5. STUDY ASSESSMENTS AND PROCEDURES

5.1. Study Flow Chart

A detailed study flow chart (with all assessments) is displayed hereafter.

Clinical Study Protocol

Study code: ABX464-004

	Screening	Days				Treatment interruption - Follow-up					
Time Window	± 7 days	± 2 days (except D25 ± 4)			± 2 days						
Days	D-21	D0	D7	D14	D21	D25	D28	Twice weekly for 3 weeks	Every week till VR	ARTs reintroduction visit	FU visit(s)***
Obtained Inform Consent	x										
Check of IN/EX Criteria	x	x									
Physical Examination	x	X	X	X	Х	X	Х		Х	X	Х
Body Weight (kg)	X	X	X	X	Х	X	Х		х	x	Х
Height Measurement (cm)	x										
Medical History	X			[
Medical Calls to patients		Day	3&5								
Serology: HBV, HCV, HIV	x										
Hematology + Biochemistry	x	x	х	x	х	x	х		х	x	X****
CD4 and CD8 count	X	х	Х	X	Х	X	Х	X	Х	X	Х
Urinalysis	X	X	Х	X	Х	X	х		X	x	
Blood Pregnancy test	X			l				1			
Urine pregnancy test	X	X	Х	X	X	X	х		X	X	
Vital signs	X	X	Х	X	Х	X	Х	1	Х	x	
ECG (12 lead)	X	Х	Х				Х			х	
DRV/RTV-COBI prescription	x	x	х	x	х	x	х			х	х
ABX464/placebo treatment dispensation and patient diary review		x	x	x	x	x	x				
Blood samples drug pK		х*	Х*	X*	Х*	X**					
Blood samples for viral load /miRNA	x	x	x	x	x	х	x	x	х	x	х
Genotyping										Х	
Leukopheresis (optional)	x									x	
Blood samples for reservoir assessment • Viral DNA		x					х			x	
TILDA Adverse Events	X	x	x	x	x	x			x	x	х
recording * pre DRV/RTV or DRV/C	DBI marning doce	^	^		^	^	^		^	^	

** pre DRV/RTV or DRV/COBI morning dose, 0.5, 1, 1.5, 2, 2.5, 3, 3.5, 4, 6, 8, 12 and 24 h post-dose (hospitalization is not required)

*** Every 14 days till undetectable VL

**** only bioschemistry required and for at least 28 days after treatment interruption

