5.2.6. Treatment interruption period Visits (\pm 2 days)

During the treatment interruption period study visits should be performed weekly until viral load rebounds. The following examination should be performed during these visits.

- Physical examination and vital signs;
- Hematology;
- Biochemistry and urinalysis;
- Viral Load, CD4/CD8 count;
- Blood collection for HIV reservoir assessment;
- Urine pregnancy test for all women of childbearing potential;
- Adverse Events reporting.

However, during the first three weeks (after treatment interruption), the Viral Load and the CD4/CD8 count should be controlled twice a week.

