9.4. Determination of Sample Size

The endpoint considered for the sample size calculation is the Time To Viral Rebound defined as the time between treatment stop (i.e. day 29) and viral rebound detection. According to published studies, the expected median Time To Viral Rebound (calculated from treatment stop) is expected to be 7 days in the 'DRV/RTV or COBI + placebo' group while it should be at least 28 days in the 'DRV/RTV or COBI + ABX464 group' in order to continue the clinical development of this new drug.

According to these hypotheses, the corresponding power was calculated using the PROC POWER of the SAS software (version 9.4). Thus, the enrolment of 28 evaluable patients at a dose level (21 in the ABX464 at 50 mg or 150 mg and 7 in the group placebo) will permit to have 80% power to detect a significant difference, at 0.05 level, between groups using the Time To Viral Rebound as end point.

Thus, the overall sample size can vary from 28 patients (in case the dose escalation procedure is not recommended) to 36 patients in case the dose escalation to 150 mg o.d. is recommended.

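### The count of patients with any abnormal laboratory or vital-sign value has no time window, yet off-treatment testing is weekly until viral rebound, so an arm that rebounds later would tend to show more abnormal patients without any drug effect

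*Protocol*

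**What the plan says.** **The summary.** Section 9.3 of the protocol states: "Number of patients with at least one abnormal values will be tabulated (counts and percents) for each parameter in summary shift tables, by group and" (the sentence closes with the dose level). The sentence covers laboratory parameters, vital signs and ECG, gives no period or visit limit, and is repeated in the synopsis under Statistical Methods. In the same section, treatment-emergent adverse events are divided into those up to Day 28 and those after it. That division is not extended to laboratory or vital-sign data. Section 9.3.1 adds laboratory statistics at each scheduled assessment and shift tables from baseline.

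**The testing schedule.** Section 5.2.6 states: "During the treatment interruption period study visits should be performed weekly until viral load rebounds". Haematology, biochemistry and vital signs are listed for those weekly visits, and again for the ART reintroduction visit (5.2.7). In the follow-up visits after that, every 14 days, the flow chart footnote reads: "only bioschemistry required and for at least 28 days after treatment interruption". Patients who do not rebound end the study 3 months after interruption (3.2).

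**The expected difference in rebound.** In section 9.4 the placebo median is "expected to be 7 days in the 'DRV/RTV or COBI + placebo' group", and for ABX464 "it should be at least 28 days in the 'DRV/RTV or COBI + ABX464 group" if development is to continue.

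**The concern.** A percentage of patients with any abnormal value rises with the number of tests per patient. Here that number is set, after Day 28, by how long the patient stays without rebound. If the drug works, ABX464 patients are tested more often than placebo patients, and the table tends to show more of them as abnormal even when each test carries the same risk in both arms. The better the drug works, the larger the spurious excess. Safety against placebo is the primary objective (section 2.1), so a table that compares arms on this count should not have its denominator of opportunities driven by efficacy.

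**Working it through.** **1. The plan's own figure.** Section 9.4 claims "80% power to detect a significant difference, at 0.05 level" with "21 in the ABX464 at 50 mg or 150 mg and 7 in the group placebo". With exponential rebound times the medians give a hazard ratio of 7/28 = 0.25. Events needed (Schoenfeld, two-sided): (1.96 + 0.84)² / (0.25 × 0.75 × (ln 0.25)²) = 7.85 / 0.360 ≈ 22. The follow-up used is not stated. Power is 79.9% at 49 days by this formula, and 78.6% at 21 days and 82.4% at 28 days by a Lakatos-type log-rank calculation. So 80% reproduces, and the two medians can be carried forward.

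**2. Expected haematology tests per patient.**
- On treatment, post-baseline: Day 7, 14, 21 and 28 = 4 tests.
- Off treatment: the weekly test in week k+1 takes place if the patient has not rebounded by day 7k. Its expected number over 13 weeks (3 months) is the sum over k = 0 to 12 of 2^(−7k/median).
- Placebo: the sum of 2^(−k) is 2.0. ABX464: the sum of 2^(−k/4) = (1 − 2^(−3.25)) / (1 − 2^(−0.25)) = 0.895/0.159 = 5.6.
- Totals: 6.0 against 9.6, or +60%. The test in the week of detection stands for the reintroduction visit.

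**3. How far the count depends on reading the schedule.** The flow chart marks haematology at Day 25. Section 5.2.4 does not list it, and the 52 mL planned for that day is used up by 13 pharmacokinetic samples of 4 mL.

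| Tests counted | Placebo | ABX464 | Excess |
|---|---|---|---|
| As in step 2 | 6.0 | 9.6 | +60% |
| Plus Day 25 | 7.0 | 10.6 | +52% |
| Plus a separate reintroduction test for every rebounder | 7.0 | 10.5 | +50% |
| Plus both | 8.0 | 11.5 | +44% |
| As in step 2, stopped 4 weeks off drug | 5.9 | 7.1 | +22% |

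In the last row the off-treatment sums run over k = 0 to 3: 1.9 and 3.1.

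**4. Other parameters.**
- Biochemistry continues every 14 days after reintroduction. At the medians (5 against 8 tests), adding the same number of follow-up visits to both arms gives 6 against 9 (+50%) with one visit and 9 against 12 (+33%) with four.
- Vital signs stop at reintroduction in the flow chart but are listed at follow-up visits in section 5.2.8.
- ECG is done at Screening, Day 0, Day 7, Day 28 and reintroduction (5.3.3), not weekly, so the mechanism does not apply.

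**5. Effect on the table with no drug effect.** The percentage with any abnormal value is the mean of 1 − (1 − p)^n over the distribution of n from step 2. The protocol gives no per-test risk p, so a range is assumed.

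| Assumed p, independent tests | Placebo | ABX464 | Both arms, to Day 28 only (n = 4) |
|---|---|---|---|
| 1% | 5.8% | 9.1% | 3.9% |
| 2% | 11.4% | 17.4% | 7.8% |
| 5% | 26.3% | 37.7% | 18.5% |

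Independence is the extreme case. With a beta-binomial model at p = 5%, a within-patient correlation of 0.1 gives 21.5% against 28.2%, and 0.5 gives 11.6% against 13.3%. With 5 and 8 tests fixed, correlation 0.5 gives 11.0% against 12.9%.

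**The case against.** The strongest reply is that a table's analysis window is ordinarily settled in the statistical analysis plan, and section 9 describes itself as a summary of what that plan will elaborate. No passage says outright that values from Day 0 to rebound will be pooled. This carries weight, but the protocol has fixed the any-abnormal count and has given a period split to adverse events and not to these data. Taken literally, the text pools. The per-visit statistics in 9.3.1 give another view of the laboratory data, but they do not correct the count and do not cover vital signs.

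The second reply is that the effect is modest. With 7 placebo patients per dose level, one patient is 1/7 = 14.3 percentage points, more than any of the gaps above (3.3, 6.0 and 11.4 points under independence). The count is descriptive, other safety reviews stand beside it, and any bias runs against the drug. All of this stands and limits the importance of the point. It does not make a systematic tilt desirable when removing it is so cheap.

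A reader might also infer that ABX464 will have 60% more tests by construction, across all safety parameters. The documents do not support that. The 28-day median is a threshold for continuing development, and without a delay in rebound there is no imbalance. The 60% applies to haematology without the Day 25 test. Biochemistry is diluted by later testing, as are vital signs if 5.2.8 is followed, and ECG is not affected.

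**Conclusion.** The concern holds in a conditional form. An any-abnormal count without a window, combined with weekly testing that ends at rebound, favours finding abnormalities in whichever arm rebounds later. Under the section 9.4 medians the expected excess in post-baseline haematology tests on ABX464 is roughly 45-60%, and about 22% if the table were limited to four weeks off drug. How much this moves the table cannot be settled from the protocol: at an assumed 5% per-test risk the gap runs from about 11 points with independent tests to about 2 points with strong correlation. The calculation assumes exponential rebound times, full attendance and no early withdrawal. The change is worth making, although the comparison it protects is descriptive and rests on few placebo patients.

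**What to change.** In section 9.3 and the synopsis, extend the Day 28 split to the any-abnormal counts and shift tables for laboratory parameters and vital signs. Make the comparison between arms on scheduled post-baseline visits up to and including Day 28, where both arms have the same planned tests. Report the interruption period in a separate table, either by scheduled week among patients still being tested or per number of tests. State whether haematology is taken at Day 25, and reconcile the flow chart with 5.2.4 on that visit and with 5.2.8 on vital signs.

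The cost is a change of wording and one more set of tables. No visits, samples or patients are added. The downside is that abnormalities after Day 28 move from the main table to a second one.
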